**Figure 3: Time to shock**

11. (Kestra Clinical Specialist) After conversion of the arrhythmia, disconnect the Test System from the adhesive pads.

12. Obtain copies of procedure documentation

- Download the manual shock log from the tablet
- Electronic or paper record of the ECG signals from the EP monitoring system (from induction through conversion)
- Study-specific physician procedure report (de-identified)

The following situations are examples of protocol deviations:

- a) Rescue shock delivered before a first or second Test System shock delivered
- b) Therapy delivered from external EP system (e.g. ATP/pacing), or CIED (ATP/shock) before a first or second Test System shock delivered
- c) No shock delivered from Test System (equipment failure or operator error)
- d) No induction attempted after enrollment due to change in patient's hemodynamic status

### **Screen Failures**

Subjects will be screen-failed if they do not meet eligibility, refuse consent to participate, or choose to withdraw consent to participate before they are enrolled as defined in paragraph 1 of this Section.

### **Handling of Withdrawals**

When a subject is withdrawn from the study for any reason, the reason(s) for withdrawal will be recorded on the appropriate case report form (CRF). For any subject who is

withdrawn due to adverse events (AEs), the reason for withdrawal must be recorded as an AE and not any other reason.

In the event of a subject death during the study, the date of death (as listed on the death certificate) will be used as the date of study withdrawal.

It is vital to obtain follow-up data on any subject who is withdrawn because of an AE. In any case, every effort must be made to undertake protocol-specified safety follow-up procedures and the site principal investigator will be required to document that follow up.

## 10 ADVERSE EVENT REPORTING

Adverse events (AEs) as defined below will be monitored during the study procedure. AEs may be reported by the subject, discovered by Investigator questioning, or detected through physical examination or other means at the study visit. All AEs must be recorded on the CRF. The following information about each AE will be collected: description, severity, onset and resolution dates, seriousness, relationship to the Test System, action taken, and outcome.

### Definitions

For the purposes of this study, an **AE** is defined as any untoward medical occurrence in a subject during the study that in the opinion of the investigator is at least possibly-related to use of the Test System during the EP procedures specified in Section 9.

A serious adverse event (**SAE**) is defined as any adverse event that:

- Leads to death
- Leads to serious deterioration in the health of a subject that:
  - Results in a life-threatening illness or injury, or
  - Results in a permanent impairment of a body structure or a body function, or
  - Requires in inpatient or prolonged hospitalization  $\geq$  24 hours, or
  - Results in medical or surgical intervention to prevent life-threatening illness or injury or permanent impairment to a body structure or function, or
- Leads to fetal distress, fetal death or a congenital anomaly or birth defect

**Adverse Device Effect (ADE)** is an adverse event related to the use of an investigational medical device (the Test System).

**Anticipated Adverse Device Effects (AADEs)** are those events related to the use of the Test System that are reasonably expected to occur as a result of the subject's participation in the study. The following are AADEs based on complications reported associated with defibrillation threshold testing (Wilkoff BL), complications associated with ICD pulse generator replacement (Poole JE), and the Test System engineering hazard analysis:

- Acute kidney injury
- Acute liver injury
- Blisters
- Burn
- Cardiac arrest
- Cardiac Perforation
- Cellulitis
- Central nervous system injury
- Death
- Deep vein thrombosis
- Depression of contractile function leading to worsening of heart failure
- Heart failure needing intravenous treatment with inotropes or diuretics
- Hematoma at catheter site requiring evacuation or long-term treatment with antiplatelet or anticoagulation medication
- Hemodynamic instability
- Hemothorax
- Hospital readmission
- Infection
- Itching under Test System defibrillation or ECG electrodes
- Lead dislodgment or malfunction (requiring re-operation)
- Myocardial Injury
- Pain persistent > 7 days
- Peripheral arterial embolus
- Persistent hypotension
- Pleural effusion
- Pneumothorax
- Prolonged hospitalization
- Pulseless electrical activity (PEA)
- Recurrent VT
- Refractory VF
- Respiratory arrest/depression
- Skin Rash
- Stroke or transient ischemic attack (TIA)
- Tamponade
- Thromboembolic events

An **Unanticipated Adverse Device Effect (UADE)** is any serious adverse effect on health or safety or any life-threatening problem or death caused by, or associated with the study device (the Test System), if that effect, problem, or death was not previously identified in nature, severity, or degree of incidence in this protocol; or any other unanticipated serious problem associated with the device that relates to the rights, safety, or welfare of subjects.

All AEs will be assessed by the investigator And the Medical Monitor according to:

- Whether the event is serious (SAE);
- The severity of the event (mild, moderate, severe);

- Mild: Awareness of signs and symptoms, but easily tolerated; are of minor irritant type, causing no loss of time from normal activities; symptoms would not require medication or a medical evaluation; signs and symptoms are transient.
- Moderate: Discomfort severe enough to cause interference with usual activities; requiring treatment, but not extended hospitalization or intensive care for the subject.
- Severe: Incapacitating with inability to do work or usual activities; signs and symptoms may be systemic in nature or require medical evaluation and/or treatment; requiring additional hospitalization or intensive care (prolonged hospitalization).
- The relationship of the event to use of the Test System:
  - Possibly Related: There is a reasonable possibility that the AE may have been primarily caused by device use. The AE has a reasonable temporal relationship to the use of the device and follows a known or expected response pattern to device, but alternative etiology is equally or more likely compared to the potential relationship to the use of the device.
  - Probably Related: There is a reasonable probability that the AE may have been primarily caused by device use. The AE has a reasonable temporal relationship to the use of the device and follows a known or expected response pattern to device. Note: this definition assumes no alternative etiology is equally or more likely compared to the potential relationship to the use of the device.
  - Definitely Related: The AE has a strong causal relationship to device use. The AE follows a strong temporal relationship to the use of the device, follows a known response pattern to the device, and cannot be reasonably explained by known characteristics of the subject's clinical state, other therapies, or change in clinical status during the electrophysiologic procedure.

Whenever possible, the Investigator should group signs or symptoms that constitute a single diagnosis under a single AE term (e.g. redness and swelling can be combined under skin irritation).

Baseline conditions are not considered adverse events unless the condition worsens because of Test System use.

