### Study Objectives and Endpoints

Efficacy Objective: To evaluate conversion efficacy of the ASSURE WCD Waveform

Primary Endpoint: Estimated cumulative first and second shock VT/VF conversion efficacy  $\geq 94\%$

Secondary Endpoint: First shock conversion efficacy (report only)

Safety Objective: To collect information on adverse events at least possibly related to use of the investigational Test System

Safety Endpoint: Summary of adverse events that are at least possibly related to use of the investigational Test System, including classification of Unanticipated Adverse Device Effects

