### **Electrophysiology (EP) Procedure**

[figure not shown]
The following procedure will be performed during a single study visit corresponding to the EP procedure. A Kestra Clinical Specialist must be present.

1. (Investigator or qualified designee) Explain the purpose and conduct of the study visits to the subject, answer the subject's questions, and obtain written informed consent. Provide the subject with a copy of the informed consent. Consent can be completed in advance of the procedure date, or on the day of the Study Visit.
2. (Investigator) Review inclusion/exclusion criteria prior to any procedural activities
3. (Investigator or qualified designee) Assign Subject ID number
4. (Investigator or qualified designee) Record demographic data and protocol-specified medical history on case report form
5. (Investigator or qualified designee in consult with Kestra Clinical Specialist)  
Position two sets of disposable adhesive defibrillation pads on the patient's torso:
  - Locate one set provided by the Sponsor in the left anterior and left-subscapular posterior positions to be connected to the Test System (see Figure 2). This configuration will be used to deliver the experimental therapeutic defibrillation shock(s).
  - Locate the other set of defibrillation pads (not provided by the Sponsor for the backup rescue defibrillator) on the subject's torso according to physician preference but separated from the Test System defibrillation

pads to prevent arching or current shunt, and at least one inch away from a CIED if applicable.

- (Kestra Clinical Specialist) Obtain anterior and posterior photographs of the torso (not including subject's head/face) to document electrode placement.
- 6. (Kestra Clinical Specialist) Create a new patient in the ASSURE WCD Monitor, enter the subject ID number, and configure the ASSURE WCD Monitor to **manual** shock mode. (**Manual** shock mode allows the Study Shocks to be delivered on command by the physician)
- 7. (Investigator or Sub-Investigator) Induce a single sustained episode of rapid VT or VF  $\geq$  150 bpm via the CIED or an electrophysiology catheter.
  - If this protocol is performed as part of an ICD replacement procedure, the test procedure must be performed prior to surgical opening of the CIED pocket.
  - If using a CIED for induction, ventricular therapy (i.e., ATP and Shocks) must be programmed OFF or temporarily suspended while therapy from the Test System is delivered.

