  - If the arrhythmia is less than 150 bpm, convert the patient's arrhythmia using the backup rescue defibrillator and/or standard of care procedures.
  - Repeated induction attempts may be performed to induce the ventricular rhythm. The investigator may stop induction attempts at any point if in their judgement it is no longer in the best interest of the patient.
  - Conversion is defined as the presence of a non-shockable rhythm (rhythms other than VT or VF) after shock delivery
- 8. (Kestra Clinical Specialist under the direction of the Investigator or Sub-Investigator) If the Arrhythmia is estimated to be greater than 150 bpm, deliver a 170J shock from the Test System.
- 9. (Kestra Clinical Specialist under the direction of the Investigator or Sub-Investigator) Deliver a second shock at 170J from the Test System if the first shock is unsuccessful.
- 10. (Investigator or Sub-Investigator) If both attempts to convert using the Test System are unsuccessful, convert the patient's arrhythmia using the backup rescue defibrillator, implantable defibrillator and/or standard of care procedures.

Time to the first shock from the Test System will be approximately 6 seconds. Total time to an external rescue shock, if needed, is estimated to be approximately 20 seconds.

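### The AE definition admits only harm attributed to the Test System, so harm attributed solely to other study acts is left out of the safety endpoint and the Medical Monitor's review

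*Combined protocol and SAP*

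**What the plan says.** **Definition (Section 10, Definitions).** An untoward occurrence is an AE only if, "in the opinion of the investigator", it is "at least possibly-related to use of the Test System during the EP procedures specified in Section 9". The opening of Section 10 lists one attribution to be collected, to the Test System. The relatedness scale has three grades (possibly, probably, definitely), all about device use. The lowest is generous: it applies when timing and pattern fit the device, "but alternative etiology is equally or more likely compared to the potential relationship to the use of the device".

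**Same limit elsewhere.** The safety endpoint in Section 7 is "Summary of adverse events that are at least possibly related to use of the investigational Test System". SAE reporting, AE follow-up and the rule on worsening baseline conditions carry the same restriction. Under Medical Monitor in Section 6, the Monitor reviews the AEs and SAEs that the investigator has already called at least possibly related.

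**Acts done for the study (Section 9, EP Procedure, step 7).** The step asks for VT or VF of at least 150 bpm and has a slower rhythm converted without the Test System. It adds: "Repeated induction attempts may be performed to induce the ventricular rhythm". No maximum is stated; stopping is left to the investigator's judgement.

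**Safety Analysis (Section 7).** This plans separate summaries of Test System-related AEs and lets the Medical Monitor's view of relatedness replace the investigator's. It also presents deaths and events leading to discontinuation, and names vital signs, examination findings and ECGs.

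**The concern.** Attribution is normally something recorded about an adverse event. Here it decides whether the event exists in the data at all, it is made once by the investigator, and it asks about one cause only. Yet the protocol exposes subjects to other study acts: induction attempts beyond those the patient's care required, backup conversion of a rhythm too slow to qualify, and suspension of implanted-device therapy.

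Two things are at stake. A reader of the safety results would take them as the harm of taking part, when harm from these acts can be missing. And the count may depend on the site: one investigator may call a complication possibly device-related and record it, while another attributes the same complication to the induction and records nothing.

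**Working it through.** The point turns on a definition, so the check traces one event through the plan.

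**Trace.** A subject counts as enrolled once the Test System is connected (Section 9, Informed Consent and Enrollment). Suppose an induction gives a rhythm below 150 bpm, which is converted by the backup route. A further attempt is made, and prolonged hypotension follows before any Test System shock. The investigator attributes it to the induction alone.

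1. *AE definition:* not met, so the event is neither an AE nor an SAE, since an SAE is a kind of AE.
2. *CRF:* Data Sources lists AEs as the only harm category. The induction attempt is captured as procedure data, but its consequence is not.
3. *Medical Monitor:* receives only events already called related, so does not see it.
4. *Safety endpoint:* the event is outside it. The subject is still in the ITT population used for safety and contributes a zero.
5. *Other routes in Safety Analysis:* the death count does not apply. Discontinuation would catch the event only if it ended participation, which is intra-procedural anyway. Vital signs and examination findings are not among the listed CRF data, and the Section 9 steps schedule neither. ECG records run from induction through conversion, so they could show only what is visible in that window.

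**Consistency of Safety Analysis with Definitions.**

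- A separate summary of Test System-related AEs has meaning only if some AEs are not related. The definition allows none.
- Precedence for the Medical Monitor works in one direction. The Monitor may disagree with a related call, although the scale has no grade in which to record that. The Monitor has no described way to restore an event that the investigator screened out.

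**Scale.** The plan states no AE rate to reproduce. Table 4 does give exact (Clopper-Pearson) intervals for 20 subjects, and their complements apply to a count of harms:

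- 20 of 20 has interval 83.2% to 100%, so 0 harmed of 20 has interval 0% to 100 − 83.2 = 16.8%. Check: 1 − 0.025^(1/20) = 0.168.
- 19 of 20 has interval 75.1% to 99.9%, so 1 harmed of 20 is 5.0% with interval 100 − 99.9 = 0.1% to 100 − 75.1 = 24.9%.

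Leaving out one affected subject therefore turns 5.0% (0.1% to 24.9%) into 0% (0% to 16.8%).

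How likely such a case is cannot be taken from the documents. If p is an assumed chance per subject, the chance of at least one case in 20 is 1 − (1 − p)^20:

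| Assumed p | Chance of at least one case in 20 |
|---|---|
| 0% (no attempts added) | 0% |
| 1% | 18% |
| 2% | 33% |
| 5% | 64% |
| 10% | 88% |

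These values show only that a single case is the relevant unit. They do not estimate the harm.

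**The case against.** The strongest reply is that the scope is deliberate. The safety objective and endpoint are stated consistently, and a single-arm device study has good reason to keep device harm apart from the background risk of the host procedure. That stands as a reason to tabulate the two separately. It is not a reason to leave study-caused harm unrecorded.

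Several stronger readings are tempting, and the documents do not support them:

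- *Induction harm can never be an AE.* The lowest relatedness grade admits events with an equally or more likely other cause. The anticipated effects are "AADEs based on complications reported associated with defibrillation threshold testing" and with generator replacement, and include perforation and catheter-site hematoma. Some induction harm can therefore be recorded. The grade still requires suitable timing relative to device use and a response pattern recognised for the device, which harm arising before any Test System shock would not readily meet.
- *The anticipated list contradicts the definition.* It does not: the list is framed as a subset of device-related events. Its procedural entries do make uneven recording between sites more likely.
- *Such harm cannot reach the safety results at all.* Deaths and discontinuation events are presented with no relatedness limit in that sentence, and Subject Disposition summarises reasons for discontinuation.
- *The withdrawal rule conflicts with the definition.* The rule for a subject "withdrawn due to adverse events (AEs), the reason for withdrawal must be recorded as an AE and not any other reason" uses the defined term, and the sentence before it has the reason recorded for any withdrawal. There is no conflict.
- *Every induction is a study act, and ICD-replacement subjects always get an extra one.* Inclusion criterion 3 enrols patients already scheduled for procedures that generally involve induction. The instruction that "the test procedure must be performed prior to surgical opening of the CIED pocket" does not say that a second induction follows; the study episode may be the planned one. Only added acts are at issue.

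**Conclusion.** The concern holds in a limited form. Harm that the investigator attributes solely to a study act other than Test System use is not an AE. It is left out of the safety endpoint and the Medical Monitor's review, and only deaths, discontinuations or ECG findings could reveal it. This happens with the plan followed exactly. The Safety Analysis section is also inconsistent with the AE definition, both in its separate summary of related AEs and in the precedence it gives the Medical Monitor.

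The size is unknown, because the documents give neither the number of added attempts nor their risk, and it is nil if no such harm occurs. If one subject is affected, the omission is 5 percentage points in a study of 20. The conclusion rests on the text of the definition and on the investigator attributing the event solely to the other act. The primary efficacy result is not touched. The change should be made, but it is not a reason to stop the study.

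**What to change.** - **Section 10, Definitions:** define an AE as an untoward occurrence during study participation that is at least possibly related to the Test System or to a procedure performed for the study. Name the latter: induction attempts added to obtain a qualifying arrhythmia, and conversion of a rhythm that does not qualify. Align the baseline-condition, SAE-reporting and follow-up wording.
- **Section 10, data collected and relatedness scale:** add a study-procedure attribution field and a category for not related to the Test System.
- **Section 6, Medical Monitor:** have the Monitor review all recorded events, so that precedence on relatedness works in both directions.
- **Section 7, safety endpoint and Safety Analysis, and the Protocol Summary:** tabulate Test System-related and study-procedure-related events separately. This also gives the planned separate summary a meaning.
- **Anticipated list:** mark which entries are procedural complications. Keep the UADE classification for the Test System.

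The cost is one CRF field, some wording in Sections 6, 7 and 10 with a matching line in the Protocol Summary, and possibly a few more reported events in their own column. The Test System-related count stays separately visible, and no clinical rule changes. Events judged related to neither cause would still go unrecorded; collecting all untoward events from enrolment to study exit would close that too, with more data entry.

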### **Medical Monitor**

The Medical Monitor (an independent physician not participating as a clinical investigator in the clinical study) will review and assess in conjunction with the Sponsor all AEs considered by the investigator to be at least possibly related to the use of the Test System to determine if they are reportable to the FDA as Unanticipated Adverse Device Effects (UADEs) per the definition in Section 10. The Medical Monitor will also review all Serious Adverse Events considered by the investigator to be at least possibly related to the use of the Test System to verify relatedness and the Serious classification.

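### Read literally, every relatedness grade requires a recognised response pattern, so a novel device effect could miss the AE record and independent UADE review

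*Combined protocol and SAP*

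**What the plan says.** **Grades (Section 10, Definitions).** Three grades are listed. Possibly Related needs a reasonable time relationship and an event that "follows a known or expected response pattern to device, but alternative etiology is equally or more likely compared to the potential relationship". Probably Related needs the same time relationship and an event that "follows a known or expected response pattern to device. Note: this definition assumes no alternative etiology is equally or more likely". Definitely Related needs a strong time relationship and an event that "follows a known response pattern to the device, and cannot be reasonably explained by" other features of the subject or procedure. There is no grade for unrelated or unlikely.

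**Entry to the safety data.** The same section limits AEs to untoward occurrences "that in the opinion of the investigator is at least possibly-related to use of the Test System". In Section 6 (Medical Monitor), the Monitor's UADE determination covers "all AEs considered by the investigator to be at least possibly related to the use of the Test System". In Section 7 (Study Objectives and Endpoints), the safety endpoint is a summary of AEs that are at least possibly related, including their UADE classification.

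**UADE definition (Section 10, Definitions).** A UADE includes a serious effect caused by or associated with the device that "was not previously identified in nature, severity, or degree of incidence in this protocol", and also any other unanticipated serious problem associated with the device.

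**Reporting.** Adverse Event Reporting Procedures requires the investigator to report UADEs to the IRB within 10 working days. Reporting UADEs to Regulatory Agencies requires the sponsor to report them to FDA and other IRBs within ten days. Neither duty refers to a relatedness grade.

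**The concern.** The UADE category exists partly to catch harm that nobody foresaw. The grades ask the rater to match an event to a response already known or expected. An effect that is new in kind may have nothing to match, and is then hard to place in any grade, even when its timing and the clinical picture point to the device.

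This matters because the same phrase, at least possibly related, controls three things: what is recorded as an AE, what the independent physician reviews for UADE status, and what the only safety endpoint summarises. The study is intended to support a premarket approval application (Section 5, Background). A UADE tally drawn from that pool would say less about novel effects than its label suggests.

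**Working it through.** No arithmetic applies. The plan gives no figure on this point and no incidence for unforeseen effects. The check is a comparison of the provisions.

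**Step 1: is the pattern a required element?** In Possibly and Probably Related it is joined to the time relationship by a conjunction, and nothing marks it as only supportive. In Definitely Related it is one item in a list of requirements, and there the word is known alone, which is narrower. Read literally, it is required in all three.

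**Step 2: which serious effects does this touch?** The UADE test asks whether the protocol identified the effect. The grade test asks whether the event fits a known or expected response to the device. These are different questions, which gives four cases.

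| Serious effect | Meets the pattern condition? | UADE by definition? |
|---|---|---|
| Listed as anticipated, of expected severity and frequency | Yes | No |
| Listed in kind, but worse or more frequent | Can | Yes, by severity or incidence |
| Not identified in the protocol, but fits a recognised response to a shock | Yes | Yes, by nature |
| Not identified in the protocol and fits no known or expected response | No, in any grade | Yes, by nature |

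Only the last row is exposed.

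**Step 3: follow a last-row event through the plan.**

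- *AE record.* The AE definition rests on the investigator's opinion and does not cite the grades. The grades are, however, the only definition of possibly related that the protocol offers. An investigator who relies on them would not call the event an AE. One who relies on general judgement could.
- *Grading.* If the event is recorded, Section 10 has both the investigator and the Medical Monitor assess its relationship to the device. No listed grade fits.
- *Medical Monitor.* Section 6 starts the Monitor's UADE determination from AEs that the investigator considers at least possibly related, so an event left out earlier does not arrive. For serious events the Monitor also verifies relatedness. Section 7 (Safety Analysis) uses the Monitor's assessment of relatedness for the summaries, so the gap is met a second time.
- *Safety endpoint.* It has the same restriction as the AE definition.
- *Direct UADE reporting.* The UADE definition has its own causal wording, and the reporting duties in Section 10 depend neither on AE status nor on a grade. This route stays open.

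**Step 4: result.** On a literal reading, three of the four downstream uses (AE record, Medical Monitor's determination, safety endpoint) can miss a last-row event. The fourth (direct reporting) does not depend on the grades.

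**The case against.** A reader might infer that the grades shut novel harm out altogether, so that it is never an AE and the UADE count is zero whatever the device does. The documents do not support that, for these reasons.

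- The AE definition turns on the investigator's opinion, and Section 10 applies the grades to events that are already AEs. That is circular, but it is not a clear bar. Possibly Related also opens by asking only for a reasonable possibility of device cause.
- The UADE definition stands on its own and includes a catch-all limb. The investigator's and sponsor's reporting duties require no grade, and the sponsor also has ongoing responsibility for safety evaluation.
- An effect missing from the protocol's list can still fit a recognised response to a shock, and would then pass the grades and be a UADE by nature. The list of anticipated effects is broad (it includes death, cardiac arrest and myocardial injury), so many new mechanisms would present as a listed event.
- Section 7 (Safety Analysis) also draws on vital signs, examination findings and ECGs, and reports deaths. A novel effect need not be invisible.

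All of this stands, and it limits the point to the last row of the table. It does not remove it. The reporting duties say what happens once someone has recognised a UADE. The independent determination described in Section 6 begins from AEs considered possibly related. Section 7 (Data Sources) lists AEs as case report form data and names no separate UADE entry. The direct route therefore does not repair the safety endpoint.

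A reader might also take Possibly Related to contradict itself, because it speaks of the device as primary cause while allowing an alternative that is equally or more likely. It does not. A 30% possibility that the device was the primary cause, against 70% for an alternative, satisfies both parts.

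**Conclusion.** The point holds as an inconsistency of wording that should be fixed. The grades, read literally, do not fit the UADE definition in the same section. A device effect that matches no known or expected response could be left out of the AE record, the safety summary and the Medical Monitor's UADE determination. The route to UADE status is weakened but not closed, and a zero count is not guaranteed.

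The conclusion rests on two assumptions: that raters treat the response pattern as required, and that investigators use the grades when forming the opinion on which AE status depends. The documents say neither expressly, but they offer no other definition of possibly related. How often such an effect would occur in 20 subjects cannot be derived from the documents, so no number is attached. The endpoint affected is descriptive. The primary endpoint and its pass/fail table are untouched.

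**What to change.** 1. In Section 10 (Definitions), make the response pattern supportive for Possibly and Probably Related, for example: a known or expected pattern supports relatedness but is not required for it. Definitely Related may keep its known-pattern element.
2. Reconcile the AE definition in Section 10 and the Medical Monitor paragraph in Section 6 with the UADE definition, so that any serious event with a reasonable possibility of device cause reaches the Monitor, whether or not it resembles a recognised response.
3. Optionally, add a not-related grade, so that the Monitor's verification of relatedness has a defined outcome when the Monitor disagrees with the investigator.

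The cost is a few sentences in the protocol and the case report form guidance, plus the IRB approval that Section 12 (Modification of the Protocol) requires for amendments. A few more events may be graded Possibly Related, so the safety table may look slightly less favourable. Sample size, the efficacy endpoints and the study procedure do not change.
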